Protocol Title: *Neo-adjuvant anti-PD-L1 therapy prior to definitive surgical resection of regionally metastatic head & neck cutaneous squamous cell carcinoma with an unknown or historic primary site: a window trial*

I have read this protocol and agree that it contains all necessary details for carrying out this study. I will conduct the study as outlined herein and will complete the study within the time designated, in accordance with all stipulations of the protocol and in accordance with Good Clinical Practices, local regulatory requirements, and the Declaration of Helsinki.

I will provide copies of the protocol and all pertinent information to all individuals responsible to me who assist in the conduct of this study. I will discuss this material with them to ensure that they are fully informed regarding the study agent(s) and the conduct of the study.

Investigator Name (print)

Investigator Signature

Date

PROTOCOL SYNOPSIS

Protocol Title

Neo-adjuvant Atezolizumab prior to definitive surgical resection of regionally metastatic head and neck cutaneous squamous cell carcinoma with an unknown or historic primary site.

Protocol Number

UCDCC#295

Phase of Development

II

Investigational Product, Dosage Form, Route, and Dose Regimen

Neoadjuvant prior to definitive surgery: atezolizumab 1200 mg IV Q3 weeks x 2 cycles

Adjuvant: atezolizumab 1200 mg IV Q3 weeks x 15 cycles (in combination with radiation therapy)

Primary Objective

Evaluate the rate of pathologic complete response (pCR) at the time of surgery following neo-adjuvant atezolizumab in patients with regionally metastatic head and neck cutaneous squamous cell carcinoma (HNSCCC):

Secondary Objectives

1) Further characterize the oncologic response to neo-adjuvant atezolizumab and adjuvant atezolizumab in combination with radiation therapy in patients with regionally metastatic head and neck cutaneous squamous cell carcinoma (HNSCCC):

- a) Determine the rate of major pathologic response (mPR) at the time of surgery.
- b) Evaluate the 2-year event free survival (EFS) after completion of adjuvant therapy.

2) Investigate the utility of conventional imaging and novel biomarkers in predicting and assessing response to neoadjuvant atezolizumab therapy.

- a) Investigate associations between pre-treatment tumor FDG avidity and response to neoadjuvant immunotherapy
- b) Evaluate the ability of fine-cut contrast enhanced CT or MRI of the head and neck to assess response to neoadjuvant immunotherapy prior to surgery.
- c) Evaluate the capabilities of serial liquid biopsy analysis of tumor-associated exosomes to predict neoadjuvant immunotherapy response.

3) Evaluate the safety and tolerability of anti-PD-L1 with atezolizumab neo-adjuvant therapy in resectable regional metastatic HNCSCC.

- a) Quantify Toxicity (adverse events) determined by CTCAE v5

Study Design and Investigational Plan / Methodology

This is a Phase II trial investigating the efficacy of the anti-PD-L1 antibody atezolizumab (Tecentriq) in the neoadjuvant setting for patients with regionally metastatic cutaneous head and neck squamous cell carcinoma with a historic or unknown primary. This will be an open-label trial with a single arm reporting response rates with pathologic response (pCR) as the primary endpoint.

Screening

Patients will be screened for eligibility based on their clinical history, imaging and pathology results obtained prior to initial consultation. Patients who meet eligibility criteria will be presented with the details of the study at their initial clinical evaluation. Patients interested in participating in the study will then be consented and enrolled by a member of the study team.

- *Clinical Evaluation*

At initial screening visit, patients will undergo a full history and physical (H&P) and comprehensive bloodwork (SoC). A Fine needle aspiration (FNA) or core needle biopsy will be performed of the involved lymph node if pathologic diagnosis has not yet obtained. Photo-documentation of the regional tumor bed will be performed.

Screening bloodwork will be obtained (See section 5.1.5) and processed through the central laboratory as per routine SoC. In addition, one 4 mL lavender-top tube will be drawn simultaneously with these scheduled blood draws for research analysis of tumor-associated exosomes.

- *Imaging*

Baseline imaging will include fine-cut contrast enhanced CT or MRI of the head and neck and a full body PET/CT. Imaging will not be repeated for patients who have already completed imaging within one month of initial consultation.

Neo-adjuvant Atezolizumab

Atezolizumab 1200 mg will be administered on Day 1 of each 21 day cycle (Q3 weeks = Q3W) in the neoadjuvant period for 2 doses. Patients will then proceed with SoC surgery, the extent dictated by initial presentation of disease status prior to administration of atezolizumab.

Pre-Dose Blood Draws

Participants will undergo blood draws at the infusion center prior to administration of neo-adjuvant atezolizumab for routine blood analysis as noted in section 5.1.5. One 4 mL lavender-top tube will be drawn simultaneously with these scheduled blood draws for research analysis of tumor-associated exosomes.

Post-neo-adjuvant Imaging

Repeat fine-cut contrast-enhanced CT or MRI imaging of the head and neck will be performed one week prior to surgery to assess response to neoadjuvant therapy. The imaging modality utilized will be the same as that modality used for screening.

Surgery and Pathologic Evaluation

All participants will undergo a curative-intent surgical resection as defined by SoC. Surgery will occur within 10 weeks of study enrollment and at least two weeks after second dose of neoadjuvant Atezolizumab. The goal of curative intent surgery for regionally metastatic CSCC involves resection to negative margins of the index lesion with the associated at-risk regional lymph nodes as determined by the study physician. An evaluation of tumor status and staging per AJCC guidelines (8th edition) will be performed on all surgical specimens. The pathologist will assess the specimen for pCR and mPR (see 10.1).

Patients demonstrating pCR at time of surgery:***Adjuvant Treatment***

Patient demonstrating pCR at the time of surgery will not receive any additional adjuvant therapy and will enter surveillance.

Imaging

PET/CT will be performed approximately 12 weeks after surgery.

Follow-up / Surveillance

Patients will be followed in otolaryngology/head and neck surgery and medical oncology clinic every 3 months for 3 years after surgery. Patients will be assessed for treatment-related side effects, cancer recurrence and blood draws performed at the cancer center for biomarkers.

In the setting of suspected clinical or radiographic recurrence per iRECIST criteria, tumor tissue will be collected by biopsy, unless not clinically feasible as assessed and documented by the investigator.

Patients with residual disease at time of surgery:

Patients with residual disease at the time of surgery will receive atezolizumab Q3W x 15 cycles in combination with SoC adjuvant radiation. SoC adjuvant radiation typically begins 6-7 weeks

after surgery and consists of 6 weeks of radiation with dosing dictated by pathologic findings. Recommendations for adjuvant radiation will be determined at a multidisciplinary tumor board where surgical pathology findings will be reviewed. Adjuvant atezolizumab will begin concurrent to adjuvant radiation and continue for 15 cycles.

Pre-Dose Blood Draws

As in the neo-adjuvant setting, participants will undergo blood draws at the infusion center prior to administration of adjuvant atezolizumab for routine blood analysis as noted in section 5.1.5. One 4 mL lavender-top tube will be drawn simultaneously with these scheduled blood draws for research analysis of tumor-associated exosomes.

Imaging

All participants will have imaging performed with PET/CT approximately 12 weeks (+/- 1 week) after completion of adjuvant RT.

Follow-up / Surveillance

Patients will be followed in otolaryngology/head and neck surgery and medical oncology clinic every 3 months for 2 years after completion of adjuvant atezolizumab. Patients will be assessed for treatment-related side effects, cancer recurrence and undergo blood draws for biomarkers.

In the setting of suspected clinical or radiographic recurrence per iRECIST, tumor tissue will be collected by biopsy, unless not clinically feasible as assessed and documented by the investigator.

Study Population & Eligibility Criteria

Participants \geq 18 years with resectable regionally metastatic HNCSCC from an unknown or historical primary. Patients must have surgically resectable disease and no evidence of distant metastatic spread. Patients cannot have a concurrent identifiable primary tumor and cannot have had previous RT in the area designated for treatment.

Sample Size and Statistical Considerations:

Simon's two-stage design (Simon, 1989) was used to determine sample size. The null hypothesis that the true response rate (pCR) is $p_0 = 0.05$ will be tested against a one-sided alternative. In the first stage, 5 patients will be accrued. If there are no responses in these 5 patients, the study will be stopped. Otherwise, 13 additional patients will be accrued for a total of 18. The null hypothesis will be rejected if 3 or more responses are observed in 18 patients. This design yields a type I error rate of 0.05 and power of 80% when the true response rate is 0.3.

Due to the nature of single arm and small sample size, we will not adjust our analyses for multiplicity but we will present all outcomes we studied in a single paper with a pre-specified designation of each outcome (e.g., primary or secondary/exploratory). Also, formal hypothesis

testing will be avoided or properly accompanied/indicated by a warning (e.g., a historical control for comparator or other comparability issues).

We will summarize continuous data at baseline with standard descriptive statistics, e.g., mean and SD (or median and IQR) and binary data with frequency and proportion. For continuous and binary outcomes data, point estimates and 95% CIs will be computed for appropriate parameter estimable (e.g., mean or median with accounting for censoring, if needed) and the Clopper and Pearson exact binomial method (with no censoring), respectively.

Longitudinal data will be summarized similarly and accompanied by time point to illustrate possible trends. When we utilize historical controls (for description and informal comparison), we will use control sample matched on key confounders (e.g., age, gender, key comorbidities and medical histories). We expect approximately 40 control patients, thus, achieving approximately 1:2 ratio in sample size for current sample: comparator.

Endpoints

Primary Endpoint

pCR

Secondary Endpoints

- 1) Oncologic response to therapy:
 - a) MPR
 - b) 2-year EFS
- 2) Imaging and biomarker assessment of response to therapy:
 - a) FDG avidity of nodal disease sites as measured by PET
 - b) ORR as measured by CT or MRI of the head and neck per iRECIST criteria
 - c) Plasma exosome levels
- 3) Safety and Tolerability assessment:
 - a) Toxicity (adverse events) determined by CTCAE v5

Duration of Study and Follow-up

1. INTRODUCTION

1.1 Background and Study Rationale

Head and neck cutaneous squamous cell carcinoma (HNCSCC) remains a challenging disease to treat. In advanced stages, it has poor disease-free survival (DFS) and overall survival (OS) (Harris 2017). Our current treatment options are limited to surgery and radiation, with limited success in advanced and regionally metastatic cases. There is a pressing need to investigate new therapeutic modalities to improve outcomes and survival.

Neoadjuvant immunotherapeutics (anti-PD-1 and anti-PD-L1) antibodies offer significant potential for HNCSCC patients, with opportunities to improve survival and disease extent. Data from a phase II study of neoadjuvant cemiplimab prior to surgery in patients with stage III/IV HNCSCC demonstrated a pCR in 55% of patients and major pathologic response in an additional 15% (Gross 2019). Patients who had a pCR were de-escalated from adjuvant radiation. The high response rate of HNCSCC is thought to be related to their high mutational burden from UV light-mediated DNA damage resulting in highly immune-responsive tumors.

A challenge for recruiting HNCSCC with previous studies for immunotherapeutics has been that many patients present with advanced, regionally metastatic disease with their primary site previously treated by their local provider (surgeon, dermatologist). Thus, these patients with aggressive, regionally metastatic disease with poor outcomes (who would likely benefit from neoadjuvant trials of immunotherapeutics), have not met criteria for any existing phase II & III clinical trials. At UC Davis, we treat a large volume of patients with this disease and have extensively studied their outcomes. Patients with regionally metastatic disease from an occult or historical primary are currently overlooked by existing HNCSCC trials but are seen at a high volume at UC Davis.

Here, we propose to address this overlooked population of regionally metastatic HNCSCC with occult or previous primary, utilizing a regimen of neoadjuvant atezolizumab (Genentech) to assess tumor response in regional nodal disease in addition to adjuvant atezolizumab added to the SoC. The data gleaned from this phase II trial may lead to later stage multicenter clinical trials, novel correlative biomarkers, and improvement and advancement of current care for patients with HNCSCC.

Encouraging clinical data emerging in the field of tumor immunotherapy have demonstrated that therapies focused on enhancing T-cell responses against cancer can result in a significant survival benefit in patients with advanced malignancies (Hodi et al. 2010; Kantoff et al. 2010; Chen et al. 2012).

The PD-L1 pathway serves as an immune checkpoint to temporarily dampen immune responses in states of chronic antigen stimulation, such as chronic infection or cancer. PD-L1 is an extracellular protein that downregulates immune responses through binding to its two receptors, PD-1 and B7-1. PD-1 is an inhibitory receptor expressed on T cells following T-cell activation, and expression is sustained in states of chronic stimulation (Blank et al. 2005; Keir et al. 2008). B7-1 is a molecule expressed on antigen-presenting cells and activated T cells. Binding of PD-L1 to PD-1 and B7-1 inhibits T-cell proliferation and activation, cytokine production, and cytolytic activity, leading to the functional inactivation or exhaustion of T cells (Butte et al. 2007; Yang et al. 2011). Overexpression of PD-L1 on tumor cells has been reported to impede anti-tumor immunity, resulting in immune evasion (Blank and Mackensen 2007). Therefore, interruption of the PD-L1 pathway represents an attractive strategy for restoring tumor-specific T-cell immunity.

Targeting the PD-L1 pathway with atezolizumab has demonstrated activity in patients with advanced malignancies who have failed standard-of-care therapies. Objective responses have been observed across a broad range of malignancies, including NSCLC, RCC, melanoma, colorectal cancer, head and neck cancer, gastric cancer, breast cancer, and sarcoma (see atezolizumab Investigator's Brochure for detailed efficacy results).

Atezolizumab has been generally well tolerated. Adverse events with potentially immune-mediated causes consistent with an immunotherapeutic agent, including rash, influenza-like illness endocrinopathies, hepatitis or transaminitis, pneumonitis colitis, and myasthenia gravis, have been observed (see Atezolizumab Investigator's Brochure for detailed safety results). To date, these events have been manageable with treatment or interruption of atezolizumab treatment.

1.2 Background on Atezolizumab

Atezolizumab is a humanized immunoglobulin (Ig) G1 monoclonal antibody that targets PD-L1 and inhibits the interaction between PD-L1 and its receptors, PD-1 and B7-1 (also known as CD80), both of which function as inhibitory receptors expressed on T cells. Therapeutic blockade of PD-L1 binding by atezolizumab has been shown to enhance the magnitude and quality of tumor-specific T-cell responses, resulting in improved anti-tumor activity (Fehrenbacher et al. 2016; Rosenberg et al. 2016). Atezolizumab has minimal binding to Fc receptors, thus eliminating detectable Fc-effector function and associated antibody-mediated clearance of activated effector T cells.

Atezolizumab shows anti-tumor activity in both nonclinical models and cancer patients and is being investigated as a potential therapy in a wide variety of malignancies. Atezolizumab is being studied as a single agent in the advanced cancer and adjuvant therapy settings, as well as in combination with chemotherapy, targeted therapy, and cancer immunotherapy.

Atezolizumab is approved for the treatment of certain lung cancers, hepatocellular carcinoma, melanoma, and others.

Refer to the Atezolizumab Investigator's Brochure for details on nonclinical and clinical studies.

2. STUDY OBJECTIVES AND ENDPOINTS

2.1 Primary Objectives

Evaluate the rate of pathologic complete response (pCR) at the time of surgery following neo-adjuvant atezolizumab in patients with regionally metastatic head and neck cutaneous squamous cell carcinoma (HNSCCC):

2.2 Secondary Objectives

1) Further characterize the oncologic response to neo-adjuvant atezolizumab and adjuvant atezolizumab in combination with radiation therapy in patients with regionally metastatic HNSCCC:

- a) Determine the rate of major pathologic response (mPR) at the time of surgery.
- b) Evaluate the 2-year event free survival (EFS) after completion of adjuvant therapy.

2) Investigate the utility of conventional imaging and novel biomarkers in predicting and assessing response to neoadjuvant atezolizumab therapy.

- a) Investigate associations between pre-treatment tumor FDG avidity and response to neoadjuvant immunotherapy

- b) Evaluate the ability of fine-cut contrast enhanced CT or MRI of the head and neck to assess response to neoadjuvant immunotherapy prior to surgery.
- c) Evaluate the capabilities of serial liquid biopsy analysis of tumor-associated exosomes to predict neoadjuvant immunotherapy response.

3) Evaluate the safety and tolerability of anti-PD-L1 with atezolizumab neo-adjuvant therapy in resectable regional metastatic HNCSCC.

- a) Quantify Toxicity (adverse events) determined by CTCAE v5

2.2 Endpoints

Primary Endpoint

pCR

Secondary Endpoints

1) Oncologic response to therapy:

- a) MPR
- b) 2-year EFS

2) Imaging and biomarker assessment of response to therapy.

- d) FDG avidity of nodal disease sites as measured by PET
- e) ORR as measured by CT or MRI of the head and neck per iRECIST criteria
- f) Plasma exosome levels

3) Safety and Tolerability assessment:

- a) Toxicity (adverse events) determined by CTCAE v5

3. STUDY DESIGN

3.1 Description of the Study

This is a Phase II trial investigating the efficacy of the anti-PD-L1 antibody atezolizumab (Tecentriq) in the neoadjuvant setting for patients with regionally metastatic cutaneous head and neck squamous cell carcinoma with a historic or unknown primary. This will be an open-label trial with pCR as the primary endpoint.

Screening

Patients will be screened for eligibility based on their clinical history, imaging and pathology results obtained prior to initial consultation. Patients who meet eligibility criteria will be presented with the details of the study at their initial clinical evaluation. Patients interested in participating in the study will then be consented and enrolled by a member of the study team.

- *Clinical Evaluation*

At initial screening visit, patients will undergo a full history and physical (H&P) and comprehensive bloodwork as per SoC. A Fine needle aspiration (FNA) or core needle

biopsy will be performed of the involved lymph node if pathologic diagnosis has not yet obtained. Photo-documentation of the regional tumor bed will be performed.

Screening bloodwork will be obtained (See section 5.1.5) and processed through the central laboratory as per routine SoC. In addition, one 4 mL lavender-top tube will be drawn simultaneously with these scheduled blood draws for research analysis of tumor-associated exosomes. This research vial will be transported by [name], [name], [name], or other approved Otolaryngology department members to the Cancer Center Biorepository for cataloging (contact: [name]), and storage as needed. Collected whole blood samples will be withdrawn and processed by [name] and collaborators when needed for subsequent analysis.

- *Imaging*

Baseline imaging will include fine-cut contrast enhanced CT or MRI of the head and neck and a full body PET/CT. Imaging will not be repeated for patients who have already completed imaging within one month of initial consultation.

Neo-adjuvant Atezolizumab

Atezolizumab 1200 mg will be administered on Day 1 of each 21 day cycle (Q3 weeks = Q3W) in the neoadjuvant period for 2 cycles (cycle length = 21 days). Patients will then proceed with SoC surgery, the extent dictated by initial presentation of disease status prior to administration of atezolizumab.

Because of the possibility of an initial increase in tumor burden caused by immune cell infiltration in the setting of a T-cell response (termed pseudoprogression) with atezolizumab treatment, clinical or radiographic progression per iRECIST may not be indicative of true disease progression. In the absence of unacceptable toxicity, patients with clinical or radiographic evidence of progression while receiving neo-adjuvant atezolizumab will be permitted to receive their second dose and postoperative adjuvant doses of atezolizumab if they meet all of the following criteria:

- Evidence of clinical benefit, as determined by the investigator following a review of all available data
- Absence of symptoms and signs (including laboratory values, such as new or worsening hypercalcemia) indicating unequivocal progression of disease
- Absence of decline in Performance Status that can be attributed to disease progression
- Absence of tumor progression at critical anatomical sites (e.g., leptomeningeal disease) that cannot be managed by protocol-allowed medical interventions

Patient who have NOT met all of the above criteria will NOT receive their second dose of neo-adjuvant atezolizumab and will proceed directly to surgery. These patients will also not receive adjuvant atezolizumab and will receive only SoC adjuvant radiation.

Pre-Dose Blood Draws

Participants will undergo blood draws at the infusion center prior to administration of neo-adjuvant atezolizumab for routine blood analysis as noted in section 5.1.5. One 4 mL lavender-top tube will be drawn simultaneously with these scheduled blood draws for research analysis of tumor-associated exosomes. This research vial will be transported by [name], [name], [name], or other approved Otolaryngology department members to the Cancer Center Biorepository for cataloging (contact: [name]), and storage as needed. Collected whole blood samples will be withdrawn and processed by [name] and collaborators when needed for subsequent analysis.

Post-neo-adjuvant Imaging

Repeat fine-cut contrast-enhanced CT or MRI imaging of the head and neck will be performed one week prior to surgery to assess response to neo-adjuvant therapy. The imaging modality utilized will be the same as that modality used for screening.

Surgery and Pathologic Evaluation

All participants will undergo a curative-intent surgical resection as defined by SoC. Surgery will occur within 10 weeks of study enrollment and at least two weeks after second dose of neoadjuvant Atezolizumab. The goal of curative intent surgery for regionally metastatic CSCC involves resection to negative margins of the index lesion with the associated at-risk regional lymph nodes as determined by the study physician. An evaluation of tumor status and staging per AJCC guidelines (8th edition) will be performed on all surgical specimen. The pathologist will assess the specimen for pCR and mPR (see 10.1). Pathology assessment will be as per standard of care documentation, including: dimensions of index lesion, total nodal number of lymph nodes removed, total positive node number (and positive nodal levels), any extracapsular extension, any perineural invasion. PD-L1 staining will be performed on a representative section from the largest positive node. Tissue will be formalin fixed and paraffin embedded and banked per standard pathology protocol.

Patients demonstrating pCR at time of surgery:*Adjuvant Treatment*

Patients demonstrating pCR at the time of surgery will not receive any additional adjuvant therapy and will enter surveillance.

Imaging

PET/CT will be performed approximately 12 weeks after surgery.

Follow-up / Surveillance

Patients will be followed in otolaryngology/head and neck surgery and medical oncology clinic every 3 months for 3 years after surgery. Patients will be assessed for treatment-related side effects, cancer recurrence and blood draws performed at the cancer center for biomarkers.

In the setting of suspected clinical or radiographic recurrence per iRECIST criteria, tumor tissue will be collected by biopsy, unless not clinically feasible as assessed and documented by the investigator.

Patients with residual disease at time of surgery:

Patients with residual disease at the time of surgery will receive atezolizumab Q3W x 15 cycles in combination with SoC adjuvant radiation. SoC adjuvant radiation will be initiated greater than 4 weeks and less than 7 weeks after surgery and consists of 6 weeks of radiation therapy with dosimetry determined by pathologic findings at the time of surgery. Recommendations for adjuvant treatment will be determined at a multidisciplinary tumor board where surgical pathology findings will be reviewed. Adjuvant atezolizumab will begin concurrent to adjuvant radiation and continue for 15 cycles.

Pre-Dose Blood Draws

As in the neo-adjuvant setting, participants will undergo blood draws at the infusion center prior to administration of adjuvant atezolizumab for routine blood analysis as noted in section 5.1.5. One 4 mL lavender-top tube will be drawn simultaneously with these scheduled blood draws for research analysis of tumor-associated exosomes. This research vial will be transported by [name], [name], [name], or other approved Otolaryngology department members to the Cancer Center Biorepository for cataloging (contact: [name]), and storage as needed. Collected whole blood samples will be withdrawn and processed by [name] and collaborators when needed for subsequent analysis.

Imaging

All participants will have imaging performed with PET/CT approximately 12 weeks after completion of adjuvant RT.

Follow-up / Surveillance

Patients will be followed in otolaryngology/head and neck surgery and medical oncology clinic every 3 months for 2 years after completion of adjuvant atezolizumab. Patients will be assessed for treatment-related side effects, cancer recurrence and blood draws for biomarker. In the setting of suspected clinical or radiographic recurrence per iRECIST, tumor tissue will be collected by biopsy, unless not clinically feasible as assessed and documented by the investigator.

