5.2.2 Patient Discontinuation from Study

Patients have the right to voluntarily withdraw from the study at any time for any reason. In addition, the investigator has the right to withdraw a patient from the study at any time. Reasons for withdrawal from the study may include, but are not limited to, the following:

- Withdrawal of consent
- Study termination or site closure
- Death
- Loss to follow up

Every effort should be made to obtain information on patients who withdraw from the study. The primary reason for withdrawal from the study should be documented in the patient's medical records. If a patient requests to be withdrawn from the study, this request must be documented in the source documents and signed by the investigator.

If a patient withdraws from the study, the study staff may use a public information source (e.g., county records) to obtain information about survival status.

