5.3 Treatment and Patient Discontinuation

Patients must permanently discontinue study treatment (atezolizumab) if they experience any of the following:

- Intolerable toxicity related to study treatment, including development of an immune-mediated adverse event determined by the investigator to be unacceptable given the individual patient's potential response to therapy and severity of the event
- Any medical condition that may jeopardize the patient's safety if he or she continues study treatment
- Investigator discretion
- Use of another non-protocol anti-cancer therapy
- Pregnancy
- Loss of clinical benefit as determined by the investigator after an integrated assessment of radiographic and biochemical data, local biopsy results (if available), and clinical status (e.g., symptomatic deterioration such as pain secondary to disease). In the adjuvant setting, any documented recurrence of tumor will be considered a treatment failure qualifying the patient for discontinuation of the study

The primary reason for study treatment discontinuation should be documented in the patient's medical records. Patient who discontinue treatment will be proceed with SoC treatment. In the neo-adjuvant setting, patient will proceed to definitive surgery with or without adjuvant therapy. In the adjuvant setting, patients will complete their adjuvant course of adjuvant radiation or chemoradiation or continue with routine surveillance. Patients who discontinue study treatment prematurely will be replaced.

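### Section 5.3 replaces every patient who stops study treatment early while section 10 names no pCR analysis set, so the fixed 18-patient Simon rule has no defined denominator

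*Combined protocol and SAP*

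**What the plan says.** - **Stopping for progression.** Under section 3.1, a patient who progresses during neoadjuvant treatment and fails any continuation criterion "will NOT receive their second dose of neo-adjuvant atezolizumab and will proceed directly to surgery". Section 5.3 also makes loss of clinical benefit a mandatory reason to stop atezolizumab, alongside toxicity, pregnancy, other medical conditions and investigator discretion. In the adjuvant phase, documented recurrence counts as treatment failure and leads to discontinuation.
- **Replacement.** Section 5.3 ends: "Patients who discontinue study treatment prematurely will be replaced". It makes no exception by reason or by phase.
- **Adjuvant phase.** Section 3.1 states: "Patients demonstrating pCR at the time of surgery will not receive any additional adjuvant therapy and will enter surveillance". Only patients with residual disease receive the 15 adjuvant cycles.
- **Decision rule.** The synopsis and section 10.2 give a Simon two-stage design: stop if none of the first 5 respond, otherwise continue to 18 and require at least 3 pCRs. The null rate is 5%, the target rate 30%, the type I error 0.05 and the power 80%.
- **Denominator.** Section 10.1 defines the pCR rate as a proportion of patients, judged at primary resection. Neither section 10 nor the synopsis names a treated, evaluable or intention-to-treat set. The one rule based on receiving a dose, in section 9.1, applies to adverse event reporting only.

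**The concern.** The Simon boundary is tied to exact counts, 5 and 18. A replacement rule changes who makes up those counts or how many there are, so the plan must say which. Here the rule can be triggered by lack of efficacy. In the adjuvant phase every stopper is already known not to have pCR, because patients with pCR receive no adjuvant drug.

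There are two ways to apply the rule. If the replacement takes the stopped patient's place among the 18, non-responders can be exchanged for new patients. That raises the pCR estimate and the type I error, and makes the stage 1 futility stop less likely. If the stopped patient stays and the replacement is added, more than 18 patients are analysed and the plan gives no cutoff for that number. With a threshold of 3 responses in an open-label trial, the choice should not be left until results are known.

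**Working it through.** **Inputs from the documents** (synopsis, section 10.2): first stage 5, stop at 0 responses; total 18, reject at 3 or more; null pCR 0.05; target pCR 0.30.

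**Assumed, because the documents give no figure:** a share u of treated patients, from 0 to 20%, is replaced and dropped, and none of them has pCR.

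**1. The plan's own design.** With X1 ~ Bin(5, p) and X2 ~ Bin(13, p),

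P(reject) = sum over x = 1 to 5 of P(X1 = x) × P(X2 ≥ 3 − x).

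At p = 0.05: 0.2036 × 0.1354 + 0.0214 × 0.4867 + 0.0012 = 0.0276 + 0.0104 + 0.0012 = 0.039. At p = 0.30 the sum is 0.806. The design reproduces, with 0.05 as the nominal cap and 0.039 as the exact size. The chance of stopping at stage 1 under the null is 0.95^5 = 0.774.

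**2. Replaced patients leave the 18.** Dropping a share u, all without pCR, leaves the responders unchanged, so the analysed null rate is 0.05/(1 − u). Patients treated to analyse 18 are 18/(1 − u).

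| u | Analysed pCR rate | Type I error | P(stop at stage 1) | Treated per 18 analysed |
|---|---|---|---|---|
| 0 | 0.0500 | 0.039 | 0.774 | 18.0 |
| 5.6% (1 in 18) | 0.0529 | 0.045 | 0.762 | 19.1 |
| 10% | 0.0556 | 0.051 | 0.751 | 20.0 |
| 20% | 0.0625 | 0.067 | 0.724 | 22.5 |

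Type I error reaches 0.05 at an analysed rate of 0.0552, that is u = 1 − 0.05/0.0552, about 9.5%.

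Effect on a reported estimate: 3/18 is 16.7% (exact 95% CI 3.6 to 41.4). With two dropped non-responders restored it is 3/20, or 15.0% (3.2 to 37.9).

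**3. Replaced patients stay and replacements are added.** Keep the stage 1 rule and the threshold of 3, put all extra patients in stage 2, and replace 13 in step 1 by N − 5. At p = 0.05 the type I error is 0.047 for N = 20 (15 in stage 2) and 0.052 for N = 21 (16 in stage 2).

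**4. All dosed patients kept, N held at 18.** If 30% is the pCR rate among all treated patients, power remains 0.806. If 30% is the rate among resected patients and 10% are not resected, the all-treated rate is 0.30 × 0.90 = 0.27 and power is 0.751.

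**The case against.** **Replacement is not deletion.** No section says a replaced patient leaves the pCR denominator, and some wording points to retention. Section 8 lets patients who stop the drug remain in follow-up. Section 10.2 counts stage 1 patients as enrolled, and section 10.1 has no evaluability filter. A section 3.1 progressor who reaches surgery yields a specimen, and pCR is fixed before any adjuvant dose, so erasing that result because of a later stop would be odd. This stands: a reader might infer that the plan drops non-responders, and the documents do not support that. Retention does not settle the matter, though, because added patients take N past 18 without a boundary, and section 12.2 says over-accrual must not occur.

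**The size is a chosen scenario.** This also stands. The 0 to 20% range is assumed, and section 5.3 also covers stops unrelated to efficacy. An early stopper with pCR who was replaced would pull the estimate the other way. A patient who completes both neoadjuvant doses and then loses resectability is not clearly covered by the replacement sentence at all.

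**Surgery after progression.** The fourth continuation criterion is "Absence of tumor progression at critical anatomical sites (e.g., leptomeningeal disease) that cannot be managed by protocol-allowed medical interventions". A reader might infer that section 3.1 therefore orders surgery on patients who can no longer benefit from it, particularly as section 5.3 adds: "In the neo-adjuvant setting, patient will proceed to definitive surgery with or without adjuvant therapy". The documents do not support that either. The criteria govern whether atezolizumab continues, and the surgical rule reads: "All participants will undergo a curative-intent surgical resection as defined by SoC". Section 5.2.2 provides that "the investigator has the right to withdraw a patient from the study at any time", section 5.3 also says "Patient who discontinue treatment will be proceed with SoC treatment", and section 8 lets the patient's best interests override staying in the study. An explicit branch for lost resectability would be clearer wording, but its absence is not a defect claimed here.

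**Conclusion.** The concern holds as an undefined denominator under a stated, unconditional replacement rule. It does not hold as proof that the plan excludes non-responders. If replaced patients are dropped and none has pCR, type I error rises from 0.039 to 0.045, 0.051 and 0.067 at assumed drop rates of 5.6%, 10% and 20%, and stays under 0.05 up to about 9.5%. If they are kept and at least 3 responses is still the rule, it is 0.047 at 20 patients and 0.052 at 21. Both effects are modest and the Simon design itself is sound. The point should be fixed because neither reading is specified and each changes the operating characteristics of a rule that turns on three responses.

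**What to change.** Two changes, to be made together:

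1. **Section 5.3:** in place of the current replacement sentence, write: *Only patients who never receive atezolizumab will be replaced.* The sentence should be changed outright. Limiting replacement only for the primary analysis would let dosed replacements enter an all-dosed set and take it past 18.
2. **Section 10.1, with a matching line in the synopsis:** *The primary pCR set, and the stage 1 set, are the first 18 (first 5) patients who receive at least one dose of atezolizumab; no resection or no specimen counts as no pCR and no mPR.*

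Cost: a protocol amendment of two sentences and no extra patients. The reported pCR rate may be slightly lower. Power stays at 0.806 if the 30% target refers to all treated patients, and is 0.751 if it refers to resected patients and 10% are unresected, so the plan should say which is meant.

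Optional wording: in sections 3.1 and 5.3, limit surgery to disease that remains resectable without distant metastasis, with other patients going to standard care.
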